**Statistical Analysis:**

All analyses are exploratory. Statistical analyses of the data collected in this study will be focused on providing tabular and graphical summaries of the levels of inflammatory markers and of the clinical features of the disease both at diagnosis and during the course of treatment. Levels of inflammatory markers will be compared between patients with active M-HLH and the control group (i.e. hematological malignancy in absence of HLH). In addition, the degree of correlation between inflammatory markers, and between inflammatory markers and the severity of clinical manifestations, response to therapy, and survival of the patients will be assessed. Analyses may also be performed to study these relationships in various subgroups of patients, depending on the demographic, genetic and clinical characteristics observed, including *a posteriori* diagnosis based on HLH-2004 diagnostic criteria (Henter et al., 2007).

Criteria for diagnosis are:

- i) Fever
- ii) Splenomegaly
- iii) Cytopenia (affecting  $\geq 2$  of 3 lineages in peripheral blood):
  - Hb  $<90$  g/L (in infants  $< 4$  weeks: Hb  $<100$  g/L)
  - Platelets  $<100 \times 10^9$ /L
  - Neutrophils  $<1.0 \times 10^9$ /L
- iv) Hypertriglyceridemia and/or hypofibrinogenemia: Fasting triglycerides  $\geq 3.0$  mmol/L; Fibrinogen  $\leq 1.5$  g/L
- v) Hemophagocytosis in bone marrow or other specimens
- vi) Low or absence NK-cell activity (according to local laboratory reference)
- vii) Ferritin  $\geq 500$   $\mu$ g/L
- viii) sCD25  $\geq 2400$ U/ml

---

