3.1 Study objectives

- To determine the levels of inflammatory markers including, but not limited to interferon gamma (IFN γ), interleukin 1 beta (IL1 β), interleukin 6 (IL-6), interleukin 10 (IL-10), interleukin 17 (IL-17), soluble IL-2 Receptor α (sCD25), C-X-C chemokine ligand 9 (CXCL9), C-X-C chemokine ligand 10 (CXCL10), C-XC chemokine ligand 11 (CXCL11), soluble CD163 (sCD163), neopterin and Tumor Necrosis Factor alpha (TNF α) in patients diagnosed with M-HLH and whenever possible, to monitor the evolution over time of these markers.
- To assess the relationship between the above-mentioned inflammatory cytokines and disease activity.
- To assess the relationship between genetic variants of the genes typically causing primary HLH and M-HLH and associated inflammatory markers.

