3.2.2 Inflammatory biomarkers- correlation

The degree of correlations between inflammatory markers and between selected inflammatory markers and markers of disease activity (lab assessments) will be investigated.

The inflammatory biomarkers are as listed in section 3.2.1 and the other laboratory assessments as defined in the protocol are listed below

- Albumin
- AST, ALT, Alkaline Phosphatase
- Basophils
- β 2-microglobulin
- Total and conjugated Bilirubin
- BUN, serum creatinine
- CRP
- D-dimers
- Hemoglobin, Hematocrit, Red blood cells, white blood cells and differential count, platelets
- Fasting triglycerides
- Ferritin
- Fibrinogen
- Lactate dehydrogenase
- NK cell activity
- Serum IgG
- Sodium

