4.1 Overall study design and plan

This is a non-interventional study designed to determine the levels of pro-inflammatory markers (as listed above) in patients diagnosed with M-HLH and to assess the relationship between the biomarkers and disease activity and prognosis during the M-HLH course. Inflammatory markers will also be measured in a group of control patients diagnosed with hematological malignancy in absence of HLH (as described above).

Data collection may be performed retrospectively if sufficient clinical information is available to allow for a meaningful interpretation of the biomarker results.

An approximate volume of 500 µl – 1 ml of serum or plasma is required per time point. Whenever possible, serum (and not plasma) should be collected, as this is the preferred matrix for the biomarker analysis.

In addition to the serum samples for the biomarker analysis, relevant information gathered by the treating physician will be collected in a data collection form. This will include information on the clinical presentation of M-HLH, the type of underlying malignancy, the date of onset of malignancy in relation to HLH manifestations, treatment regimen prior to and/or ongoing at the time of M-HLH onset, laboratory parameters, M-HLH disease activity (e.g. newly diagnosed, reactivation), specific HLH therapy with best response to the therapy, other concomitant medications, patient follow-up and disposition, stem cell transplant status, duration of response, and survival. Whenever possible, collection of serum samples for biomarker analysis and relevant information should occur at M-HLH diagnosis, at regular time intervals during the treatment course, at resolution and/or reactivation of the disease.

In addition to the above a minimum of 1 ml of whole blood will be collected (EDTA tubes) for genetic characterization and identification of the presence of genetic variants of the genes typically causing primary HLH. A specific consent for genetic testing must be given by the patient. Genetic samples may also be collected from existing bank of samples (frozen whole blood in EDTA or frozen extracted DNA), if proper consent has been obtained.

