12.2 Inflammatory biomarkers - correlations

The degree of correlations between inflammatory markers and between inflammatory markers and laboratory assessments (potential markers of disease activity) will be assessed.

The correlations to be performed are:

1. All inflammatory biomarkers vs. all other inflammatory biomarkers as listed in section 3.2.1
2. Biomarkers relevant for emapalumab (i.e. CXCL9, CXCL10, IFN γ and sIL2R α) vs. all laboratory assessments as listed in section 3.2.2

The correlations will be evaluated by plotting biomarker scores i.e., CXCL9 vs. CXCL10 (for all combinations) in scatter plots. In the scatter plots the groups (HLH and non-HLH) will be represented by different colors. The biomarker value closest to the date of HLH diagnosis will be used if more than one sample available. For the non-HLH group the minimum and maximum value will be displayed with different markers. If just one value available that value will be displayed with another marker.

Data will be investigated to confirm normal or log-normal distribution of the parameters. If normal, the actual values will be plotted. If not normal, log-transformed values will be plotted.

The correlated samples should be within a time frame of three days.

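### SAP 12.2 promises the degree of correlation but specifies only scatter plots, so no coefficient or precision is reported; how control minima and maxima are paired within the three-day window is also unclear.

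*SAP*

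**What the plan says.** The second objective in SAP 3.1 is: "To assess the relationship between the above-mentioned inflammatory cytokines and disease activity". For this the protocol's Statistical Analysis section undertakes to assess "the degree of correlation between inflammatory markers, and between inflammatory markers and the severity of clinical manifestations". SAP 3.2.2 repeats the undertaking: "The degree of correlations between inflammatory markers and between selected inflammatory markers" and laboratory markers of disease activity will be investigated. SAP 12.2 again says the degree will be assessed, and then names the method: "The correlations will be evaluated by plotting biomarker scores i.e., CXCL9 vs. CXCL10 (for all combinations) in scatter plots".

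SAP 8 excludes statistical tests and lists the summaries for continuous data: n, mean, SD, median, quartiles, minimum and maximum. No measure of association is among them. SAP 14 names two departures from the protocol: the two markers without data, and genetics.

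On which values are plotted, 12.2 takes one date-chosen value per HLH patient, the one closest to diagnosis. For controls it says: "For the non-HLH group the minimum and maximum value will be displayed with different markers". Then: "If just one value available that value will be displayed with another marker". It ends with a time rule: "The correlated samples should be within a time frame of three days".

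**The concern.** A scatter plot shows the shape of a relation. It does not state its strength, and it does not show how uncertain that strength is with at most 19 or 20 patients. Section 12.2 is where the SAP addresses its second objective, and as written it would produce a large set of pictures to be judged by eye. SAP 2 foresees use of these analyses in submissions or manuscripts. Under SAP 5.2, a coefficient added later would have to be labelled post hoc, although the protocol promised the degree of correlation.

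The control display raises a second question. HLH values are chosen by date, but control values are chosen by size, separately for each marker. A control's lowest CXCL9 and lowest CXCL10 may come from different samples. Two programmers who both follow 12.2 could draw different control plots from the same data.

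**Working it through.** **1. Is a degree measured anywhere?** The plan states no coefficient or precision, so there is no figure to reproduce. The text decides this part: the degree is promised in the protocol's Statistical Analysis section and in SAP 3.2.2 and 12.2; the method in 12.2 is plots; the list in SAP 8 has no coefficient; SAP 14 is silent. The protocol mentions tabular and graphical summaries first and adds the degree of correlation as a further item.

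**2. How many plots?** SAP 3.2.1 lists 11 measures: 11 × 10 / 2 = 55 pairs. Section 12.2 adds four named markers (five if both IFNγ assays count) against the laboratory list in 3.2.2. That list has 24 items, or 28 if the differential is split into four more cell types: 4 × 24 = 96 to 5 × 28 = 140. Total: 151 to 195 plots.

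**3. What would an interval show?** Approximate 95% interval for Spearman's coefficient: tanh[atanh(r) ± 1.96 × √((1 + r²/2)/(n − 3))].

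For r = 0.5 and n = 19: SE = √(1.125/16) = 0.265; atanh(0.5) = 0.549; limits tanh(0.030) and tanh(1.069), that is 0.03 to 0.79. For n = 20: 0.05 to 0.78. If only 14 pairs fall within three days (assumed): −0.08 to 0.83.

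**4. Control pairing.** The number of samples per control (k), the within-patient correlation (ICC) and the share of controls with one sample are not in the documents and are assumed here. The simulation has 20 controls, two unrelated normal markers and 6,000 repetitions per case. The figure is the mean Pearson r over all control points at ICC 0.5.

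| Reading of 12.2 | k = 2 | k = 3 | k = 5 |
|---|---|---|---|
| Min with min, max with max; all controls have repeats | 0.17 | 0.33 | 0.50 |
| Same; half have one sample | 0.12 | 0.23 | 0.37 |
| Same; half have one sample; three-day rule drops extremes from different samples | about 0.09 | about 0.13 | about 0.18 |
| Both markers from the same sample | 0.00 | 0.00 | 0.00 |

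At ICC 0.8 the first row falls to 0.07, 0.15 and 0.25, and the second to 0.05, 0.10 and 0.18.

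Hand check of the first cell: the mean of the larger of two standard normals is 1/√π. Minima lie below and maxima above the centre for both markers, which creates a covariance of 0.5 × 1/π = 0.16 against a variance of 0.5 + 0.5 × 1 = 1. So r is about 0.16, close to the simulated 0.17.

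Within one symbol (minima alone, or maxima alone) the mean r is about 0 when every control has the same number of samples.

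**The case against.** The best defence is that the plan is openly descriptive. The protocol calls all analyses exploratory and names no correlation statistic, 12.2 says plainly that correlations are judged from plots, and all data are listed by patient, so nothing is hidden. This stands as far as it goes: the choice is disclosed in the SAP, and its absence from section 14 is a modest point. But excluding tests does not exclude a descriptive coefficient, and a promise to assess degree is not met by output that contains no measure of degree.

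Four stronger readings are tempting, and the documents do not support them.

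- **That 12.2 has no pairing rule at all.** It has the three-day sentence, and matching by date is a natural reading of it. What is missing is how it applies to values chosen by size.
- **That the control plots are biased.** The slope appears only under one reading and only for controls with repeat samples. Minimum, maximum and single values also carry different markers, so a reader can separate them, and a pooled r is not a planned quantity.
- **That the wide range at n = 19 is harm done by the plan.** It is sampling error, which a coefficient would not reduce. It shows only why an interval is useful.
- **That 12.2 fails because SAP 4.1 aims "to assess the relationship between the biomarkers and disease activity and prognosis during the M-HLH course".** That is a question about time course. One sample per patient does not answer it, and this point does not rest on it.

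A further fair objection is that several hundred intervals invite reading as tests. That is a real cost and is taken up in the fix.

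**Conclusion.** The main point holds on the text alone, without assumptions: the degree of correlation is promised, only plots are specified, and no strength or precision will be reported in either group for the 151 to 195 marker pairs. This merits correction because the second objective depends on it, and the remedy is a cheap improvement.

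The control pairing is an ambiguity, not a demonstrated bias. For unrelated markers its possible size at ICC 0.5 runs from 0.00 (same-sample matching) to 0.50 (all controls with five samples, minima paired with minima and maxima with maxima). It is smaller with a higher ICC or fewer repeat samples. All these values rest on assumed k, ICC and single-sample share. HLH points are unaffected.

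A minor related difference: 12.1 requires the HLH value to be after diagnosis, and 12.2 leaves this out.

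**What to change.** In SAP 12.2:

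- Use one index sample per patient, chosen by date. For HLH patients apply the 12.1 rule, including that the sample is after diagnosis; for controls, for example, the first available sample.
- Take all biomarkers from that sample, and laboratory values nearest to it within three days. Otherwise treat the pair as missing.
- Report Spearman's coefficient, the number of pairs and a 95% interval separately for HLH patients and controls, as 12.4 already separates the groups. Label them descriptive and unadjusted. Spearman's coefficient does not depend on the raw-or-log choice in 12.2, and it treats the LLOQ/2 substitutions of 8.4.2 as ties.
- If the minimum/maximum display stays in 12.2, state that both markers of a point come from the same sample and which marker anchors it. Do not compute coefficients on those points: even same-sample matching on extremes overstates a real association somewhat (a true −0.5 gives −0.49, −0.53 and −0.57 for k = 2, 3 and 5 at ICC 0.5).
- If the sponsor prefers plots only, list that in section 14 as a change from the protocol.

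Cost: SAP wording and a little programming, with no new data. There would be at most 20 control points per plot instead of up to 40, and the intervals will be wide. Two groups give 302 to 390 intervals. If no markers were related, about 12 (302 × 0.041, the simulated rate at n = 19) to 20 (390 × 0.05) would exclude zero by chance, so the text must say that they show precision only.

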12.3 Genetic variations

Not enough data available.

12.4 Subgroup Analyses

Data will be stratified and presented separately for HLH patients and non-HLH patients (i.e. control group). No additional subgroup analysis will be performed.

13 Safety analyses

Not applicable, study is observational.

13.1 Adverse events

Not Applicable as adverse events are not collected.

13.2 Laboratory data

A subset of the laboratory data collected will be displayed in scatter plots the same way as the biomarker data described in section 12.1 grouped by HLH and non-HLH group. The lab data to be plotted are:

- AST, ALT, Alkaline Phosphatase
- Total and conjugated Bilirubin
- CRP
- D-dimers
- white blood cells and differential count, platelets
- Ferritin
- Fibrinogen
- Lactate dehydrogenase

For the HLH group the value closest to the date of HLH diagnosis (value must be after HLH diagnosis) will be used if more than one sample is available. For the non-HLH group the minimum and maximum value will be displayed in different colours/markers. If just one value available that value will be displayed with the same colour/marker as the HLH group.

Laboratory data will be summarized by group using descriptive statistics and presented for HLH patients, non-HLH patients and overall.

All laboratory data will be listed by patient.

13.3 Vital signs

Weight and Height are only collected at screening/ICF. They will be presented as part of the Demographic table (see Section 10.1).

14 Changes from the planned analyses in the clinical trial protocol

No data reported for C-XC chemokine ligand 11 (CXCL11) and interleukin 17 (IL-17), hence no analyses performed for these biomarkers.

Genetic information was only obtained from 5 out of 19 HLH patients, no analysis on genetic variants will be performed.

15 References

N/A
